5. SAMPLE SIZE CONSIDERATIONS

The primary amebiasis outcome for this study is to compare the proportion of patients/subjects with resolution of diarrhea by Day 7 of therapy, in which placebo is expected to have a clearance rate of approximately 15-20%. Sample size calculations for both primary endpoints are based on a two-sample, two-sided binomial test for proportions, with alpha set to 0.05. Calculations were performed using the R statistical package (Version 3.0.2; <http://www.r-project.org>). The primary amebiasis endpoint in this aim is to compare the resolution of diarrhea between the two study arms to demonstrate that auranofin increases resolution of diarrhea. For this power analysis, we assume the following: a predicted diarrhea resolution rate of at least 80% (based on treatment results with current standard therapy with metronidazole [1]) in the auranofin treatment group.

With these assumptions, assuming 10% attrition (determined from the average of multiple other clinical trials in the same Mirpur district), a sample size of 68 with amebiasis (34 per arm; 60 completers in total) achieves greater than 95% power to detect a difference between the group proportions of 60%. The high statistical power for the primary endpoint is planned to also ensure adequate power for the secondary endpoints.

For the primary giardiasis endpoint of proportion of subjects with clearance of Giardia by Day 5, a similar sample size of 34 per arm will achieve 85% power to detect a 40% difference between treatment arms with a predicted clearance rate of 70% (based on response rates to metronidazole or tinidazole, Gardiner, 2001) and a 30% clearance rates in placebo.

6. GENERAL STATISTICAL CONSIDERATIONS

6.1. General Principles

Continuous variables will be summarized using the following descriptive statistics: n (non-missing sample size), mean, standard deviation, median, maximum and minimum. The frequency and percentages (based on the non-missing sample size) of observed levels will be reported for categorical measures. In general, all data will be listed, sorted by disease group, site, treatment and subject, and when appropriate by visit number within subject. In general, summary tables will be created separately for the four populations (asymptomatic amebiasis, asymptomatic giardiasis, symptomatic amebiasis, and symptomatic giardiasis), and will include columns for each treatment in the order (Auranofin, Placebo) and will be annotated with the total population size relevant to that table/treatment.

6.2. Timing of Analyses

There will be no planned interim analyses for efficacy or futility conducted for this study, but the DSMB may modify this during ongoing safety monitoring.

Asymptomatic subjects (34) enrolled under Versions 1-4 of the protocol will have their data reviewed and clinical database locked for analysis first and a separate report generated. This may be generated before follow-up is completed in the symptomatic study population.

In the event that recruitment and follow-up for either the Giardiasis arm or the Amebiasis arm is completed ahead of the other, the primary and secondary endpoints may be analyzed for that arm using the specified methods. This report will be considered the interim CSR and will contain detailed unblinded information about the participants, their immunological response to treatment as well as their side effects and any laboratory abnormalities. The interim CSR will be followed with a release of data corresponding to the report.

6.3. Analysis Populations

The primary analysis population is the modified Intention-to-Treat (mITT) population, described in 6.3.1 below. All primary and secondary endpoints will be conducted on both the modified Intention-to-Treat population and the per-protocol population, described in Sections 6.3.1 and 6.3.2, respectively. Tabular listings of all subjects excluded from each of these populations are provided, separately for each disease group, in [Listing 7](#) and [Listing 8](#).

6.3.1 Modified Intention-to-Treat (mITT) Population

In this study, the primary analysis will be performed on the mITT population. This population was defined in the protocol to include study participants who were randomized and dispensed at least one dose of study medication. However, as described in section 6.3.1.1 below, those who failed the eligibility criterion regarding testing positive for amebiasis or giardiasis will be excluded. Excluding subjects who were not dispensed study medication has the potential to introduce bias in estimates if the dispensation of medication is influenced by treatment assignment. Although this study is not perfectly blinded, the procedures for distributing medication are designed to reduce the possibility of un-blinding the staff dispensing medication (see Section 4.4.3). These procedures ensure that study staff dispensing medication will not be able to identify the treatment assignment of subjects prior to dispensing the first dose of treatment. Therefore, it is

unlikely that bias will be introduced by excluding subjects who did not receive at least one dose. The possibility of bias will be assessed by comparing dispensation rates between the treatment and control groups.

6.3.1.1. Exclusions Due to Violation of Eligibility Criteria

Furthermore, subjects who meet the primary outcome at baseline (and therefore should not have been enrolled) will be excluded from the mITT population. In the asymptomatic population, the outcome is a negative microscopy or antigen test at Day 5 or 7, so subjects were required to have both positive microscopy result and positive test result for their respective disease in order to enroll. Those who did not will be excluded.

In the symptomatic population, subjects were to have amebiasis or giardiasis identified by rapid EIA and positive antigen detection at enrollment in order to be eligible. The primary outcome is resolution of diarrhea by Day 5 or 7. Those who either failed the eligibility criterion (i.e., had a negative EIA or negative antigen test), or did not have diarrhea at enrollment, will be excluded from the mITT population.

6.3.2. Per Protocol Population

As a secondary analysis, a per-protocol (PP) population will be analyzed. The per-protocol population will consist of all data from subjects who did not substantially deviate from the protocol during the time leading up to (and including) the collection of the data point in question. Missed or out-of-window stool samples from prior visits will not be considered protocol deviations as long as the stool sample for the visit of interest (for a particular outcome) is provided within window. For example, if a stool sample was not provided on Day 3, but is provided on Day 5, this stool sample will be included for analysis of endpoints on Day 5. Subjects who completed at least 80% of the treatment regimen will be included in the per-protocol population. This corresponds to at most a single missed dose during the course of treatment, since the amebiasis group has seven required doses (and $6/7=86\%$) and the giardiasis group has five required doses (and $4/5=80\%$). If a large number of subjects missed a single dose, we will perform sensitivity analysis by also analyzing the population of subjects with 100% compliance. Endpoints that are measured out of window will be excluded from this analysis.

All exclusions described in Section 6.3.1.1 (Exclusions due to violation of eligibility criteria) also apply to the PP Population.

Subjects may also be removed from this population as determined on a per-subject basis by the PI and the DMID Scientific Lead prior to unblinding.

6.3.3. Safety Population

The safety population will consist of all subjects who received any study product (including control). This population will be summarized according to the actual treatment received.

6.4. Covariates and Subgroups

All analyses will be performed separately for the two disease groups (amebiasis and giardiasis). Apart from disease strata, the protocol does not formally define any subgroup analyses, and the study is not adequately powered to perform subgroup analyses.

6.5. Missing Data

The primary analysis involves comparison of a binary response between the treatment group and the placebo group. This is true for both asymptomatic and symptomatic populations, whose primary outcomes are parasitological response and resolution of diarrhea, respectively. Within each population, the response is measured at Day 7 for the amebiasis group and Day 5 for the giardiasis group. In the symptomatic population, subjects who terminate their treatment regimen and receive metronidazole due to worsening symptoms will be imputed as treatment failures for the primary outcome. That is, they will be imputed as still symptomatic by Day 7 in the amebiasis group, and by Day 5 in the giardiasis group. Secondary outcomes measured at Days 3, 5, and 7 will be imputed analogously, with the exception of the quantitative trophozoite/cyst load.

The rest of the text in this section applies to both asymptomatic and symptomatic populations.

In the primary analysis, no covariates are included, so the analysis involves two variables: the binary predictor (treatment/placebo) and the binary response (parasitological response: yes/no). Some subjects may have missing values for the response variable, for example, if they are unable to provide a stool specimen on the designated day. If all subjects are equally likely to have missing response values, then the data are Missing Completely At Random (MCAR), in which case these subjects may be dropped from analysis without biasing the results. If, on the other hand, missingness depends on other values which are observed, then the data are Missing At Random (MAR). It is possible that the data in this study will be MAR but not MCAR (which is a more stringent condition). For example, it is plausible that subjects in the auranofin group will be more likely to miss a stool specimen than those in the placebo group since constipation is one known possible side effect of auranofin. If this is the case, and if those who are missing response values in the auranofin group also experience a different response to treatment than those who remain in the study, then dropping these subjects from analysis will bias the estimate of the treatment effect. An appropriate approach to remove the bias from dropping these subjects from analysis is multiple imputation, which is proposed below. A third possibility for the missingness mechanism is that the missingness depends on one or more unobserved variables (and may depend on observed variables, as well). As all relevant symptom variables, as well as demographic variables, will be measured, it is unlikely that missingness pattern will depend on an unobserved variable. For the symptomatic population, microscopy results will also be evaluated as a predictor.

Multiple imputation will be used to handle missing response values for the primary analysis. Multiple imputation is a method in which observed covariates are used to predict missing values, and the uncertainty arising from this imputation procedure is incorporated into final treatment effect estimates. Single imputation methods, such as imputing treatment failures for all missing results, result in unrealistically small standard errors as the imputed counts are less variable than real data. In contrast, multiple imputation methods can provide valid standard error estimates. Multiple imputation methods fill in missing values repeatedly, creating multiple sets of completed datasets. For each of the datasets, point estimates and standard errors are computed. These estimates and standard errors are then combined to obtain the multiple imputation estimate and standard error estimate [2].

As our response variable is binary, logistic regression will be used for the multiple imputation procedure. In order to determine which covariates to include as predictors of missingness, tests of association between all baseline variables and missingness will be performed (t-tests, chi-square tests, or Fisher's exact tests, as appropriate). If appropriate, t-tests will be performed on transformed data, although sample size is likely large enough that transformation will not be required. Covariates whose p-values are greater than 0.10 will be included in the imputation model. Symptom variables including constipation, diarrhea, anorexia, nausea,

abdominal pain, whether or not the subject had any other AE, and whether or not the subject withdrew from the study due to an AE will be evaluated for inclusion through the same criterion. For the symptomatic population, microscopy results will be evaluated as well.

Next, the imputation procedure proceeds as follows:

1. *Imputation step.* In this step, multiple copies of the original data set are generated, and missing values of the response variable in each copy are imputed based on a logistic regression model which includes baseline variables as predictors as well as study variables measured after baseline. The imputed data sets will vary in their imputed values but will have identical non-missing values. The generation of multiple imputed data sets enables us to quantify the uncertainty arising from the imputation process.
2. *Analysis step.* On each imputed data set, the primary analysis will be performed: computing the difference in proportions of parasitological response between treatment and placebo arms, as well as the standard error for the difference in proportions. The odds ratio and respective standard error will be computed as well.
3. *Combination step.* The imputed data sets are combined to obtain a single estimate for the difference in proportions and standard error, and a single estimate for the odds ratio and standard error.

The secondary analysis includes a per-protocol analysis including only participants with completely observed data. This analysis requires the data to be MCAR, a more stringent condition than MAR.

All except one of the secondary outcomes are also binary, so will be analyzed through the same imputation method. The sole numeric outcome is parasite load, measured at multiple time points and analyzed with a mixed effects model for longitudinal data. The mixed effects model, described below, adjusts for data that are missing at random (MAR), so imputation is not required in that analysis.

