5.2 Subject Exclusion Criteria

Subjects meeting any of the following exclusion criteria at baseline will be excluded from study participation within 1 week of the initial visit:

1. Known intolerance of auranofin or gold compounds.
2. Pregnant or breastfeeding women or women of reproductive potential not using effective contraception or who plan to become pregnant or breastfeed at any given time during the study or within 3 months of study completion.
3. Use of metronidazole within the past 7 days.
4. Has any condition that would, in the opinion of the site investigator, place the subject at an unacceptable risk of injury or render the subject unable to meet the requirements of the protocol.
5. Concurrent participation in other investigational protocols or receipt of an investigational product within the previous 30 days.
6. History of alcohol or drug abuse within the last five years.

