6.6 Concomitant Medications/Treatments

Whenever a concomitant medication or study agent is initiated or the dose changed, investigators must review the concomitant medications' and study agents' most recent package inserts or investigator's brochure to obtain the most current information on drug interactions,

contraindications, and precautions. Administration of any medications, therapies, or vaccines will be recorded on the appropriate data collection form. Concomitant medications will include all current medications and medications taken within the previous 30 days through the end of the follow-up period and will be reported in the electronic case report form (eCRF). Prescription and over-the-counter drugs will be included as well as herbals, vitamins, and supplements.

Use of new medication should prompt evaluation for the presence of a new diagnosis or chronic medical disease or condition.

There are no drugs that are prohibited because of their interactions with Ridaura, but current systemic metronidazole are an exclusion criterion. There are no medications whose dose should be adjusted because of this short course of Ridaura treatment. Any patients with clinically significant underlying renal, hepatic, or immunologic abnormalities will be excluded before enrollment.

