8 STUDY PROCEDURES/EVALUATIONS

8.1 Clinical Evaluations

Medical History: Complete medical history will be obtained by interview of the subjects at the screening visit (Visit 00B) and will be reviewed and updated on Day 1 (Visit 01) prior to the first study product administration. Subjects will be queried regarding a history of significant medical disorders of the head, eyes, ears, nose, throat, mouth, cardiovascular system, lungs, gastrointestinal tract, liver, pancreas, kidney, urologic system, nervous system, blood, lymph nodes, endocrine system, musculoskeletal system, skin, and genital/reproductive tract. A history of any allergies, cancer, immunodeficiency, psychiatric illness, substance abuse, and autoimmune disease will be solicited. At follow-up visits after the first dose, an interim medical history will be obtained, when indicated, by interview of the subjects noting any changes since the previous visit.

Concomitant Medications: Concomitant medications will include a review of all current medications and medications taken within 30 days prior to signing the informed consent form and through approximately 30 days after the first study product administration. Prescription and over-the-counter drugs will be included as well as vitamins and supplements. Assessment of eligibility will also include a review of all permitted and prohibited medications per the Subject Inclusion and Exclusion Criteria (see Section 5).

Physical Examination and Vital Signs: A physical examination limited to vital signs (blood pressure, pulse, temperature), observation for rashes or glossitis, and an abdominal exam will be performed at screening (Visit 00B). On Day 1 (Visit 01) prior to the first study product administration and at follow-up visits after the first administration of study product, a targeted physical examination will be performed, if indicated, based on subject's interim medical history.

Adverse Events: Subjects will be interviewed to determine the occurrence of unsolicited AEs.

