11.2 Sample Size Considerations

The primary amebiasis outcome for this study is to compare the proportion of subjects with resolution of diarrhea (less than 3 loose stools/ 24 hours) by Day 7 of therapy, in which placebo is expected to have a clearance rate of approximately 15-20%. Sample size calculations for both primary endpoints are based on a two-sample, two-sided binomial test for proportions, with alpha set to 0.05. Calculations are performed using the R statistical package (Version 3.0.2; <http://www.r-project.org>). The primary amebiasis endpoint in this aim is to compare the resolution of diarrhea between the two study arms to demonstrate that auranofin increases

resolution of diarrhea. For this power analysis, we assume the following: a predicted diarrhea resolution rate of at least 80% (based on treatment results with current standard therapy with metronidazole, Pherson, 1984) in the auranofin treatment group.

With these assumptions, assuming 10% attrition (determined from the average of multiple other clinical trials in the same districts), a sample size of 68 with amebiasis (34 per arm; 60 completers in total) achieves greater than 95% power to detect a difference between the group proportions of 60%. The high statistical power for the primary endpoint is planned to also ensure adequate power for the secondary endpoints.

For the primary giardiasis endpoint of proportion of subjects with resolution of diarrhea by Day 5, a similar sample size of 34 per arm will achieve 85% power to detect a 40% difference between treatment arms with a predicted clearance rate of 70% (based on response rates to metronidazole or tinidazole, Gardiner, 2001) and a 30% clearance rates in placebo.

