In general, analyses will incorporate the modified intent-to-treat (mITT) principle. Participants who are "randomized and receive at least one dose of study medication" will be included in the mITT population. Subjects who terminate their treatment regimen and receive metronidazole due to worsening symptoms will be imputed as treatment failures for the primary outcome. That is, they will be imputed as still symptomatic by Day 7 in the amebiasis group, and by Day 5 in the giardiasis group. Secondary outcomes measured at Days 3, 5, and 7 will be imputed analogously, with the exception of the quantitative trophozoite/cyst load. Multiple imputation may be used to adjust for missing data in the primary and secondary analyses on the mITT population. All results will be reported as point estimates (odds ratios or mean differences across groups, as appropriate) and interval estimates (95% confidence intervals). All tests of significance for the secondary outcomes will be 2-sided and no adjustments will be made for multiple comparisons. A p-value of 0.05 will be considered statistically significant. The Statistical Analysis Plan (SAP) will provide further details. In case the language in this section differs from the language in the SAP, the SAP takes precedence.

In the event that recruitment and follow-up for either the Giardiasis arm or the Amebiasis arm is completed ahead of the other, the primary and secondary endpoints may be analyzed for that arm using the specified methods. This report will be considered the interim CSR and will contain detailed unblinded information about the participants, their immunological response to treatment as well as their side effects and any laboratory abnormalities. The interim CSR will be followed with a release of data corresponding to the report. In order to maintain the blind and allow appropriate follow up of the remaining arm, no endpoint data for the remaining arm will be included in the interim CSR and no data related to that arm will be released. An amendment to the interim CSR will provide primary and secondary analysis of the remaining arm when all primary and secondary endpoint data are available for the second arm. The official reports will be drafted by Emmes and reviewed by the PI and DMID prior to finalization. Additional information regarding the methods will be provided in the study SAP.

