3.2.2. Symptomatic Population Endpoints

Primary Outcome Measures

1. Proportion of subjects with positive rapid EIA and positive antigen detection EIA for *E. histolytica* and resolution of diarrhea (less than 3 loose stools/ 24 hours) by Day 7.
2. Proportion of subjects with positive rapid EIA and positive antigen detection EIA for *Giardia* and resolution of diarrhea (less than 3 loose stools/24 hours) by Day 5.

Secondary Outcome Measures

1. *E. histolytica*:

- a. Proportion of subjects with positive rapid EIA and positive antigen detection EIA for *E. histolytica* and trophozoites on smear at enrollment with parasitological response (no detection of trophozoites on microscopic exam) by Day 7.
- b. Proportion of subjects with positive rapid EIA and positive antigen detection EIA for *E. histolytica* and trophozoites on smear at enrollment with parasitological response (no detection of trophozoites on microscopic exam) by Day 3 and 5.
- c. Rate of decrease of trophozoite/cyst load by qPCR in stools by Days 3, 5, and 7
- d. Proportion of subjects with negative stool antigen test by Days 3, 5, 7, and 14
- e. Proportion of subjects with sustained cure (no detection of trophozoites by microscopic exam) at 14 and 28 days
- f. Proportion of subjects with relapse (same strain) or re-infection (new strain) with positive stools at 14 and 28 days by genotyping the initial vs. subsequent strain
- g. Time to resolution of diarrhea (less than 3 loose stools/24 hours)

2. *Giardia*:

- a. Proportion of subjects with positive rapid EIA and positive antigen detection EIA for *Giardia* and trophozoites on smear at enrollment with parasitological response (no detection of trophozoites on microscopic exam) by Day 3 and 5
- b. Rate of decrease of trophozoite/cyst load by qPCR in stools by Days 3 and 5
- c. Proportion of subjects with negative stool antigens by days 3 and 5.
- d. Proportion of subjects with sustained cure (no detection of trophozoites by microscopic exam) at 14 and 28 days
- e. Proportion of subjects with relapse (same strain) or re-infection (new strain) with positive stools at 14 and 28 days by genotyping the initial vs. subsequent strain
- f. Time to resolution of diarrhea (less than 3 loose stools/24 hours)

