4.3.1.2. Exclusion Criteria, Asymptomatic Population

Subjects meeting any of the following exclusion criteria at baseline will be excluded from study participation within 1 week of the initial visit:

1. Known intolerance of auranofin or gold compounds.
2. Pregnant or breastfeeding women or women who plan to become pregnant or breastfeed at any given time during the study or within 2 months of study completion.
3. Diarrhea (> 3 loose stools/ 24 hours) within 7 days prior to starting study medications.
4. Anticipated travel of more than 50 km from study site planned in next month.
5. Current use of systemic antibiotics or metronidazole.
6. Has any condition that would, in the opinion of the site investigator, place the subject at an unacceptable risk of injury or render the subject unable to meet the requirements of the protocol.
7. Concurrent participation in other investigational protocols or receipt of an investigational product within the previous 30 days.
8. History of alcohol or drug abuse within the last five years.

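### The failure rule covers only metronidazole taken after stopping the regimen for worsening symptoms, so a resolution after any other active drug counts as a success of the assigned arm

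*SAP*

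**What the plan says.** The symptomatic primary outcome in SAP 3.2.2 is "resolution of diarrhea (less than 3 loose stools/ 24 hours) by Day 7" for amebiasis, and the same by Day 5 for giardiasis. It carries no condition on other treatment, and SAP 4.5.1 has diarrhea assessed by self-report at each visit.

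One rule overrides the observed status. SAP 6.5 says that "subjects who terminate their treatment regimen and receive metronidazole due to worsening symptoms will be imputed as treatment failures for the primary outcome", and Protocol 11.4 has the same rule. It has three parts: the regimen is stopped, metronidazole is received, and the reason is worsening symptoms.

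Other medication is treated as follows:

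- Protocol 5.2 item 3 excludes "Use of metronidazole within the past 7 days".
- Protocol 6.6 says: "There are no drugs that are prohibited because of their interactions with Ridaura, but current systemic metronidazole are an exclusion criterion".
- Protocol 8.1 calls for a "review of all permitted and prohibited medications per the Subject Inclusion and Exclusion Criteria".
- Protocol 5.1 allows chronic or as-needed medication, subject only to a judgement about safety.

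Concomitant medications are recorded (Protocol 6.6), summarized by treatment group (SAP 9.8) and listed with start and end days (SAP Listings 35 and 36). No efficacy definition uses them.

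**The concern.** The sponsor has already decided that an improvement after rescue should not be credited to the assigned arm, but wrote that decision for one drug and one route to it. The protocol itself describes other drugs as active. Tinidazole helps support the giardiasis response assumption in 11.2, "with a predicted clearance rate of 70% (based on response rates to metronidazole or tinidazole", and sections 2.2 and 2.3.2 discuss nitazoxanide, albendazole, quinacrine and furazolidone. Metronidazole taken while the regimen continues, or for a reason other than worsening, also falls outside the rule.

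If such use is commoner on placebo, the placebo response rises and the difference shrinks. If it is commoner on auranofin, auranofin gains another drug's effect. Differential use is possible because the placebo capsules lack the imprint, and Protocol 5.3.2 accepts that subjects and staff could notice. If the rule is left open until after unblinding, the classification of a primary outcome could be chosen with the results in view.

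**Working it through.** **Does another provision close the gap?** Four come close, and none does.

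- Investigator discretion in Protocol 5.2 item 4 acts only at entry.
- Withdrawal because response evaluation would be disturbed (Protocol 5.3.3) can leave a missing outcome. Under SAP 6.5 that goes to multiple imputation, not to failure.
- The per-protocol population (SAP 6.3.2) has no medication criterion. It allows case-by-case removal before unblinding, but it is a secondary analysis.
- The sensitivity section (SAP 6.5.1) deals only with missing data.

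**Plan's own power.** Inputs from Protocol 11.2 and SAP 5: two-sided 0.05, 34 per arm, 60 completers, giardiasis 70% vs 30%, amebiasis 80% vs 15-20% (20% used here). Exact enumeration of all 2x2 tables, counting those with Fisher p ≤ 0.05:

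- Giardiasis: 83.8% (30 per arm), 86.0% (31), 87.6% (34). The plan states 85%, which is reproduced at 30-31 per arm.
- Amebiasis: 99.8% (30 per arm). The plan states more than 95%, which is confirmed.

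**Effect of other drug use on placebo.** The documents give no frequency, so the use fraction u is an assumption. Users are assumed to respond at the plan's active rate:

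- Giardiasis placebo rate = 0.30(1 − u) + 0.70u; auranofin stays at 0.70.
- Amebiasis placebo rate = 0.20(1 − u) + 0.80u; auranofin stays at 0.80.

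| u | Giardiasis placebo | Power, 34/arm | Power, 30/arm | Amebiasis placebo | Power, 34/arm | Power, 30/arm |
|---|---|---|---|---|---|---|
| 0% | 30.0% | 87.6% | 83.8% | 20.0% | 99.9% | 99.8% |
| 2% | 30.8% | 86.0% | 82.1% | 21.2% | 99.9% | 99.7% |
| 5% | 32.0% | 83.5% | 79.3% | 23.0% | 99.8% | 99.5% |
| 10% | 34.0% | 78.9% | 74.1% | 26.0% | 99.5% | 98.9% |
| 20% | 38.0% | 68.1% | 62.4% | 32.0% | 97.7% | 95.8% |
| 30% | 42.0% | 56.1% | 49.6% | 38.0% | 93.2% | 88.6% |

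**A harsher assumption, as a bound.** Suppose a share c of would-be non-responders takes another drug and every one of them resolves. With 30 per arm and c = 10, 20, 30%:

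- Same c in both arms: giardiasis power 74.3, 63.5, 52.8%; amebiasis 98.9, 96.3, 91.1%. Equal use still shrinks the giardiasis difference from 40 to 36, 32 and 28 points.
- Placebo arm only: giardiasis 65.5, 43.3, 23.5%; amebiasis 98.1, 91.5, 76.3%.

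**The case against.** The rule matches the only rescue the protocol provides. At each visit from Day 2 to Day 14, worsening diarrhea may lead to stopping the dose and giving standard-of-care metronidazole (Protocol 7.3). Visits take place in hospital until diarrhea resolves, and no section provides for any other antiprotozoal on study. Scoring the observed outcome regardless of other drugs is also a legitimate choice of estimand. This stands as far as it goes: use of other drugs is a possibility, not something the documents report. But the plan has not chosen the observed-outcome estimand, because it already overrides observed status for one drug and is silent on the rest.

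A second objection also stands. Because the capsules can be told apart, scoring discretionary drug use as failure could favor auranofin if placebo subjects are treated more readily. The fix must allow for that.

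A reader might infer more than the documents support on four counts:

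- That anyone given another drug is a success. Such a subject is scored on observed diarrhea, and one who does not resolve stays a failure.
- That the symptomatic criteria are in error because the asymptomatic ones excluded "Current use of systemic antibiotics or metronidazole". That was a different population with a parasite-clearance endpoint. Drug use before entry is also balanced in expectation by randomization.
- That Protocol 8.1 promises a list of drugs barred during the study. The sentence concerns eligibility, and Section 5 does hold medication content beyond metronidazole.
- That widening the rule also repairs parasite load and sustained cure. SAP 6.5 exempts quantitative load and reaches secondary outcomes only at Days 3, 5 and 7, so Day 14 and 28 sustained cure is untouched even for metronidazole.

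**Conclusion.** The point holds as a gap in the definition of the primary outcome for both symptomatic disease groups: the plan does not say how a resolution after non-study active treatment is scored unless the three conditions for metronidazole are met. Literally applied, it is a success of the assigned arm.

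The size is unknown. On the assumption that placebo users respond at the plan's active rate, the loss of power is material for giardiasis only at use of about 10% or more: from 88% to 79-56% with 34 per arm, or from 84% to 74-50% with 30 per arm, over 10-30% use. At 2-5% use with 34 per arm, power stays close to the stated 85%. Amebiasis keeps 89% or more on that model; it drops below that only under the harsher placebo-only bound (76.3% at c = 30%). It would be too strong to infer that the trial is underpowered or its comparison compromised, because no document gives a rate of such use. Severity: should-fix.

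**What to change.** **Primary rule.** In SAP 6.5, which by Protocol 11.4 takes precedence, score as failure for the primary outcome any symptomatic subject who receives metronidazole or another non-study antiprotozoal-active drug between first dose and the Day 5 or Day 7 endpoint. Identify these drugs from a coded concomitant-medication list fixed before unblinding. The drugs named as active in Protocol 2.2, 2.3.2 and 11.2 are a starting point.

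**Sensitivity analyses.** Add one that also scores as failure any antidiarrheal or systemic antibiotic started in that window. Add another that uses observed diarrhea status regardless of other drugs.

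**Reconciliation.** Protocol 5.2 item 3 refers to use in the past 7 days, 6.6 to current systemic use, and 8.1 to prohibited medications under Section 5. These should be reconciled with each other. No clinical rule on permitted drugs is proposed.

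**Cost.** SAP wording and a coded list; start and end days are already captured. A few more subjects in either arm become failures, and the first sensitivity analysis will count some antibiotics given for unrelated illness. Because the capsules are distinguishable, drug use that differs by arm could bias the primary rule toward auranofin; comparison with the observed-status analysis would show this.
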